For the secondary outcome of pain, we will use a between-groups linear mixed model for repeated measures (LMMrm) to estimate the between-group difference in the mean within-subject change from baseline to the end of the placebo controlled trial (0-3 months) and again to explore change from 3 to 12 months in the open label extension. Narcotic and non-narcotic pain medication use will enter the model as time-dependent covariates. Separately, treatment group differences in the cumulative narcotic and non-narcotic drug exposure in the 3-month placebo-controlled phase will also be estimated with linear mixed model for repeated measures. This analysis addresses the two questions, “Do patients treated with TPTD show more rapid reduction in reported pain level than those not so treated? If so, when?”

For the secondary outcome of lower limb physical function, we will use a between-groups linear mixed model for repeated measures (LMMrm) model for the analysis to estimate the difference in within-subject change from 0 to 3 months in the CSPP score in the two groups. A secondary analysis for this aim will explore the changes in physical function from 3 to 12 months in the two groups.

If TPTD can improve fracture healing, this study will have an impact on the treatment of persons with pelvic fracture who are not surgical candidates and often face severe pain, chronic immobility, and loss of function in the elderly. A positive finding of accelerated healing of pelvic fractures would also encourage study of TPTD for treatment of other osteoporotic fractures.

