fracture patients given 1-84PTH were healed within 12 weeks compared to 68% of the controls. However, there is not sufficient evidence at this time to recommend routine use of PTH peptides for fracture healing. Pelvic fractures are ideal to study for the impact of Teriparatide (TPTD) on rate of fracture healing because there are no surgical repairs for the vast majority of the fractures. Prior studies of TPTD on wrist fracture healing were limited and confounded by the increased prevalence of surgical fixation to treat these fractures. Strong evidence of pelvic fracture healing that may result from this study may not only have an impact on pelvic fractures but perhaps may indicate a potential use for other fractures as well.

In our proposed randomized, double blind, placebo controlled clinical trial in patients >65 years of age with acute pelvic fracture, we plan to evaluate whether treatment with daily subcutaneous TPTD 20 mcg/day compared with placebo, in addition to standard treatment (pain management, bed rest and prevention of complications from comorbid conditions), is effective in accelerating fracture healing in women and men compared to standard treatment alone. We hypothesize that development of a successful adjunctive therapy (TPTD) will accelerate radiographic evidence of fracture healing and speed functional recovery. If this hypothesis holds true, it would lead to a change in clinical practice and an improved quality of care for pelvic fracture patients. Evidence of an impact on the healing of pelvic fractures may also extend to a potential to improve healing of other osteoporosis-related fractures. In the planned trial we will recruit women and men with acute pelvic fractures and address 3 specific aims over 3 months of treatment in a placebo controlled double blind study to determine if **TPTD** in addition to standard care **versus placebo** and standard care:

1. Results in **earlier evidence of cortical bridging** on routine radiographs followed by confirmatory Focus CT, a novel method to reduce radiation exposure from CT scans (primary outcome).
2. Leads to **a faster reduction in pain** as assessed by both the Numeric Rating Scale and a reduction in the use of narcotics (secondary outcome).
3. Leads more to a more rapidly **improved functional outcome** using a short physical performance battery to assess lower extremity function (secondary outcome).

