**Table 2: Schedule of Procedures**

Procedure	SCR	D1	4 wk	8 wk	12 wk	6 mo	9 mo	12 mo
MMSE, Informed consent	X							
Medical history, medication list and other lifestyle	X							
Physical examination, including height and weight	X							
Screening labs (25(OH)D, PTH, Cr, Ca, prior alkaline phosphatase)	X							
Pelvic radiographs (^until healing occurs-standard care)	X		X^	X^	X^			
Pelvic limited focus CT scan (* as indicated based on cortical bridging and until healing occurs)	X full		X*	X*	X*			
Bone turnover		X	X	X	X			

Calcium for safety		X	X	X	X	X	X	X
Loading dose vitamin D (50,000 IU)	X							
Calcium (total intake 1000 mg) /1000 IU vitamin D		X	X	X	X	X	X	X
Dispense TPTD 20 mcg/day or placebo (blinded for 3 months, then open label TPTD)		X	X	X	X	X	X	X
Adverse event and concomitant medications		X	X	X	X	X	X	X
Numeric Rating scale (NRS) for pain and narcotic use survey and pill count		X	X	X	X	X	X	X
Lower extremity physical function (CSPPS and TUG)		X	X	X	X	X	X	X
Self-reported questionnaires (ADL and SF-36)		X	X	X	X	X	X	X
Telephone calls will occur weekly			X	X	X			

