**Statistical Plan:** There will be no interim analysis and missing outcome data will not be imputed. Statistical analysis will be performed using SAS software (Cary NC). Between group differences at baseline will be compared with t-tests or Wilcoxon rank sum tests and chi-square tests as appropriate (p-value <0.05 for significance). Randomization by the method of randomly permuted blocks will be created for gender and BP use groups. Our primary analysis is ITT analysis and our primary outcome (SA#1) is the categorization of the level of bridging seen on focus CT into the scores from 0 to 4, described above between 0 and 3 months. The difference in cortical bridging will be evaluated by a 2x5 chi-square (group x score) with a trend test (Jonckheere-Terpstra) to see whether TPTD treated "trend" to have more higher bridging scores than the placebo group. We expect 30% - 50% superiority with TPTD at 3 months. This categorical outcome will be further analyzed with generalized estimating equations (GEE) for longitudinal repeated measures assuming a Poisson distribution with weighting from logistic regression analysis of the missingness pattern. Secondary analyses of covariates, sensitivity analyses and the "per protocol" analysis will incorporate the aforementioned approach into this aim's GEE analysis. This analysis addresses the question "Do patients treated with TPTD show more rapid fracture healing than those given placebo? For SA #2, we anticipate that the difference in pain score between the TPTD and placebo groups in the proposed study will be > 30% at each monthly time point (0-3 months). We will use a between-groups linear mixed model for repeated measures (LMMrm) to estimate the primary outcome of the difference in the mean within-subject change from baseline in the two groups at the end of the placebo controlled trial (0-3 months) and again to explore change from 3 to 12 months in the open label extension. In addition, narcotic and non-narcotic pain medication use will enter the model as time-dependent covariates. This analysis addresses the two questions, "Do patients treated with TPTD show more rapid reduction in reported pain level than those not so treated? If so, when?" For SA#3, the CSPPS is the outcome. A linear mixed model for repeated measures (LMMrm) will be used with fixed effects of treatment group (TPTD vs. placebo), time (D1, 4-, 8- and 12-wk) and their interaction, the baseline level of the CSPPS and days from injury to randomization entered as covariates, and a within-subject covariance structure selected by empirical methods prior to hypothesis testing. This plan will be repeated for the "per protocol" analysis in which subjects are limited to those showing 80% or greater compliance over the 12-week trial. This statistical plan addresses the two clinical questions, "Do patients treated with TPTD recover lower limb function faster than those not so treated? If so, when?" LMMrm will be used to analyze data from 3-12 months and assess group by time interaction. We will group on prior BP exposure strata to account for possible heterogeneity in the R-side covariance structure.

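### The CSPPS model uses the Day 1 score as both response and covariate, and the pain model adjusts for analgesic use after randomisation, so neither estimates its stated target properly

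*Combined protocol and SAP*

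**What the plan says.** **Physical function (SA#3).** The Statistical Plan in section 7 specifies a linear mixed model with treatment, "time (D1, 4-, 8- and 12-wk) and their interaction, the baseline level of the CSPPS and days from injury to randomization entered as covariates". The choice of covariance is left open until the data are in hand, since the plan calls for "a within-subject covariance structure selected by empirical methods prior to hypothesis testing". In Table 2 the row for CSPPS and TUG is first marked at D1, with nothing at screening. The Protocol Summary gives the target: "to estimate the difference in within-subject change from 0 to 3 months in the CSPP score in the two groups". The Sample Size Justification names an unstructured covariance for the mixed model behind its TUG power figure.

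**Pain (SA#2).** Aim 2 in section 2 expects a faster fall in pain "as assessed by both the Numeric Rating Scale and a reduction in the use of narcotics". The Statistical Plan fits a mixed model to the change in pain score and adds that "narcotic and non-narcotic pain medication use will enter the model as time-dependent covariates"; the Protocol Summary says the same. The Summary also states that "treatment group differences in the cumulative narcotic and non-narcotic drug exposure in the 3-month placebo-controlled phase will also be estimated". The clinical question posed is whether reported pain falls faster on TPTD, and when.

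**The concern.** **CSPPS.** The D1 score is the only baseline, so the model partly predicts a number from itself. What follows depends on two choices left open: which covariance is picked, and which contrast is read. The possible results are a fit that does not exist, a week-12 difference with too many false positives, or a valid change contrast that discards the precision baseline adjustment should bring. The plan expects about 80 completers, and section 7 says other outcomes will be analysed in the same way, so the specification may be carried over to them.

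**Pain.** Analgesic use after randomisation is something treatment is expected to change. Holding it fixed removes or distorts part of the effect being asked about. The analysis of cumulative drug exposure describes drug use; it does not recover the total effect on pain.

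**Working it through.** **The plan's own figures.** There is no power figure for CSPPS or pain. The TUG figure (33 and 36 per group) cannot be reproduced, because the week-4 and week-8 TUG means and the correlation are not given.

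**Inputs.** From the plan: 40 per arm (80 completers, 1:1), and responses at D1 and weeks 4, 8 and 12. Assumed: SD 1; compound symmetry with correlation r = 0.3, 0.5 or 0.7; effects 0, 0.4, 0.5 and 0.6 SD at the four visits; two-sided alpha 5%.

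**1. Covariance with a free D1 variance.** Set the baseline slope to 1 and the days-from-injury coefficient to 0. Every D1 residual is then exactly zero, and the D1 variance can shrink without limit. On one simulated data set, with the D1 residual SD held at 1, 0.1, 0.01, 0.001 and 0.0001, the log-likelihood was -371.6, -200.6, -16.6, 167.6 and 351.8, while the slope went from 0.64 to 1.0. Each later tenfold step adds 184.2 = 80 × ln 10, so there is no maximum. A choice of covariance by likelihood-based fit would favour this degenerate case.

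**2. Compound symmetry, week-12 group difference.** D1 and the later visits are forced to share one residual variance. At r = 0.5 the fitted slope averages about 0.63:
- D1 residual variance: (1 - 0.63)² = 0.137
- later visits: 1 + 0.63² - 2 × 0.63 × 0.5 = 0.767
- pooled: (0.137 + 3 × 0.767)/4 = 0.609
- model SE: √(0.609 × 2/40) = 0.175
- actual SE: √(0.767 × 2/40) = 0.196

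The effective critical value is 1.96 × 0.175/0.196 = 1.75, a two-sided type I error of about 8.0%. Simulation gave 7.6%.

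**3. Compound symmetry, change from D1.** The common slope cancels from this contrast. In simulation it equalled the raw change-score difference to about 1e-15. In units of 2/40, its variance is 2(1 - r), against 1 - r² with D1 as covariate only. The relative efficiency is (1 + r)/2.

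At r = 0.5 and 0.6 SD the SE is √(1 × 0.05) = 0.224, and power is Φ(0.6/0.224 - 1.96) = 76%.

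Simulation of the model as written (6,000 runs per setting):

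| | r = 0.3 | r = 0.5 | r = 0.7 |
|---|---|---|---|
| Type I, week-12 difference | 7.1% | 7.6% | 8.3% |
| Type I, change from D1 | 5.1% | 4.8% | 5.6% |
| Type I, interaction | 5.2% | 5.2% | 5.3% |
| Power, change from D1 | 62% | 76% | 93% |
| Power, D1 as covariate only | 79% | 85% | 95% |
| 80 × (1 + r)/2 | 52 | 60 | 68 |

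A separate set of 2,000 runs gave 8.6% and 8.8% for the week-12 difference at r = 0.5 and 0.7. With AR(1) data and fit at 0.7, it was 12.4% and the change contrast was 7.7%. Model misspecification contributes there, so those runs are not used to compare power.

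**4. Main effect averaged over visits.** Including D1 gives (0 + 0.4 + 0.5 + 0.6)/4 = 0.375 SD, against 1.5/3 = 0.50 SD without it. The estimate is diluted by 25%, but its test is not distorted (5.1 to 5.3%).

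**5. Pain.** Let underlying pain be U = -ΔT + e with e of SD 1, analgesic use M = aU + v, and reported pain Y = U - bM. The unadjusted treatment coefficient is -Δ(1 - ab). The coefficient adjusted for M is -Δ(1 - R²), with R² = a²/(a² + SD(v)²). The ratio of adjusted to unadjusted is (1 - R²)/(1 - ab):

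| a | b | SD(v) | R² | Ratio |
|---|---|---|---|---|
| 0.5 | 0.3 | 0.5 | 0.50 | 0.50/0.85 = 0.59 |
| 1 | 0.3 | 1 | 0.50 | 0.50/0.70 = 0.71 |
| 1 | 0.5 | 1 | 0.50 | 0.50/0.50 = 1.00 |
| 0.5 | 1 | 1 | 0.20 | 0.80/0.50 = 1.60 |
| 0.5 | 1 | 2 | 0.059 | 0.941/0.50 = 1.88 |

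A separate set of mediation scenarios gave ratios of 0.61 to 0.97. The documents supply none of these inputs.

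**The case against.** - **Effect size.** The power loss depends on an assumed modest effect. The plan's only functional benchmark is TUG: (54.3 - 22.9)/18 = 1.74 SD. At that size and 1% alpha, the change contrast has power that rounds to 100% at all three correlations. At 1.0 SD and 5% alpha it is 96% against 99.6% (r = 0.3) and 99.3% against 99.9% (r = 0.5). This stands: the cost is material only if the CSPPS effect is modest and the correlation not high. But TUG is not CSPPS, and the benchmark comes from a study that section 3 calls neither randomised nor blinded.
- **Contrast.** The excess false positives affect a week-12 difference that the plan does not name, while the stated change contrast is valid under compound symmetry. This is right. However, the plan also asks when a difference appears, and a visit-specific group difference is a natural answer to that.
- **Failed fit.** An unbounded likelihood would probably be noticed before testing. That is likely, but the repair would then be improvised rather than pre-specified.
- **Pain.** The wording in section 7 might imply a first model without analgesic use. It does not clearly say so, and the Protocol Summary reads as one model. In the scenarios examined the adjusted coefficient has the right sign and is zero when there is no effect. The fault is therefore in the meaning and size of the estimate, not in false positives.

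**Conclusion.** Both parts hold; the primary bridging analysis is unaffected.

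The CSPPS model is wrong as written. It has no valid fit under unstructured or any other covariance with a free D1 variance. Under compound symmetry the week-12 difference rejects about 7 to 9% of the time at nominal 5%. The change contrast keeps its level there but has 65 to 85% of the efficiency of a baseline-adjusted analysis for r = 0.3 to 0.7. The efficiency ratio does not depend on effect size; the power figures do, and they rest on the assumed effects and correlations.

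The planned pain coefficient does not answer whether TPTD patients report less pain. It may be too small or too large, depending on how closely analgesic use tracks pain and how far it masks it. The 0.59 to 1.88 range is illustrative only.

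**What to change.** **CSPPS.** Choose one of two forms:
- responses at weeks 4, 8 and 12 only, with D1 as covariate plus a baseline-by-time term and days from injury; or
- D1 kept as a response with a common mean across arms, and the baseline covariate dropped.

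Pre-specify an unstructured covariance and name the week-12 contrast. In 3,000 unstructured-fit simulations under the same assumptions, power was 80 / 87 / 96% for the first form and 80 / 88 / 96% for the second (type I error of the second 5.6 / 5.3 / 5.1%). A plain change score had 62 / 75 / 93%.

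**Pain.** Make the model without analgesic covariates the main analysis. Keep the planned cumulative-exposure analysis beside it, and report the adjusted model only as a labelled sensitivity analysis.

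**Cost.** Wording only, with no new data. The main pain result will include any effect of differing analgesic use, which is why exposure is reported alongside. The common-mean form relies on randomisation to make the D1 means equal. The change should be made before unblinding.
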